9.3.2.1 Dosing patients beyond progression

An important clinical observation in the last decade is that immune activation does not necessarily result in complete cancer regression for all patients, but nonetheless, clinical improvements are observed. In this context and for elderly patients with R/R AML, unfit for intensive chemotherapy and with no alternative treatments available for their disease, achieving stable disease and/or becoming transfusion independent, together with performance status improvement, can be viewed as a positive signal. Thus, where in the investigator's opinion, the patient's disease is considered "clinically stable" with clear improvement in the patient's symptomatology and with no other treatment options available,

other than palliative care, it may be in the patient's best interests to remain on treatment with bemcentinib.

Therefore, patients experiencing disease progression are permitted to continue treatment with bemcentinib where the investigator believes patients may continue to derive clinical benefit from continued treatment.

Clinical benefit in this context is defined as meeting one or several of the following criteria: evidence of disease stabilization after documented initial progression (patient is stably worse), tolerance of drug(s), absence of rapid progression based on peripheral or bone marrow blasts and clinical hematology and clinical chemistry parameters, maintenance of good performance status (PS of 2 or less and not deteriorating], absence of worsening clinical symptoms (i.e., no symptomatic deterioration) and/or improvements in patient's quality of life).

Importantly, the decision to continue treatment must be discussed and agreed by the treating investigator, the patient and the Sponsor. All decisions will be documented in writing. Patients dosed beyond progression will continue to be evaluated for potential clinical benefit and safety. This will not affect the time point of disease progression from the perspective of trial analysis.

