## 5 Statistical Methodology

### 5.1 Planned Analyses

Disposition analyses will be carried out using the Enrolled Population. Demographic and baseline characteristics analyses will be carried out using the Safety Analysis Set. Safety analyses will be carried out using the Safety Analysis Set. Efficacy analyses will be carried out using the Efficacy Analysis Population.

Summary statistics will be presented for continuous variables, by way of n, mean, standard deviation (SD), median, minimum (Min) and maximum (Max) and by way of group frequencies and percentages for categories of categorical variables. No statistical comparison of dose levels or treatment groups will be performed. Percentages will be calculated using the total patients per dose cohort in the given population unless otherwise noted.

All data from this study will be presented in data listings. All listings will be sorted by dose level or treatment group and patient.

Baseline will be defined as the last assessment prior to study drug administration. Typically this will be Cycle 1 Day 1. Where calculated, absolute change from baseline will be presented using the following formula for each parameter: Value at the visit/timepoint – value at baseline.

Data will be presented by dose/cohort and overall in Part A and by treatment group (AML (B1: BGB324 400/200 mg Single agent; B2: BGB324 400/200 mg + Cytarabine; B3: BGB324 400/200 mg + Decitabine; B5: BGB324 400/200 mg + Cytarabine) and MDS (B4: BGB324 400/200 mg) ) and overall in Part B.

Where appropriate, the data for patients who received the MTD during Part A will be combined with that for patients who received the MTD in Part B for the purpose of data summarisation. A clear distinction will be made in the relevant Tables to differentiate between the cohort who received the MTD during the dose escalation phase of Part A, the MTD cohort from the cohort expansion phase in Part A, and the combined MTD cohort.

Any patient treated with bemcentinib beyond disease progression will be followed for the same safety and efficacy assessments as for all other patients enrolled into the study. The data for patients treated beyond progression will be presented in both a combined output (with all patients) and a separate output (reflecting a new period of analysis with the data collected in this period). All data collected will be included in the study CSR and may be presented at congress/symposia.

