For subjects in Part B a new period (treated beyond disease progression) will be created if the date of progression < date of any intake of the bemcentinib, to identify patient treated with bemcentinib beyond disease progression and also the visit cycle where the data are collected beyond the disease progression. The data collected during this period will be identified to be added in this analysis.

For Part B analysis, some outputs such as disposition, demographic and baseline characteristics, cancer history, ORR, AE and ECG(QtCF), the data for cohort B2 and B5 will be summarized together.

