## 5.7 Efficacy Analysis

The endpoints to be analysed in the efficacy analysis are:

**Objective response rate [ORR]** : Proportion of patients with a best objective response such as, CR (Complete Remission), Cri (Complete Remission with Incomplete hematologic Recovery), CRp (Complete Remission with Incomplete Platelet Recovery), CRh and PR(Partial Remission) for AML patients and CR, PR, MR(Marrow Response), PMR(Partial Marrow Response) for MDS patients;

CRh is defined as, CR (<5% myeloblasts and 0% blasts in the peripheral blood) with partial hematologic recovery, defined as meeting CR criteria but with ANC > 0.5 10^9/L and platelets > 50 10^9/L responses for patients with AML.

Best Objective Response (BOR) = Best response obtain during the study participation for a patient;

**Disease control Rate (Objective Response + SD) [DCR]**: Proportion of patients with a best objective response such as, CR, CRi, CRp, CRh and PR for AML patients and CR, PR, MR, PMR for MDS patients, + SD (stable disease) as an estimate of clinical benefit;

The ORR will be summarized by;

- Age group (<75 years, >= 75);
- AML Disease Cytogenetic Profile (Favourable, Intermediate, Adverse and not done);

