## Relapse Free Survival [RFS]

Relapse free survival [RFS]: defined as the months from the date of response until the date of relapse as confirmed by blast counts assessment (date of the disease progression will be used since disease progression is based in blast count assessment) .

Relapse Free Survival is defined only for subjects with a best objective response of CR/CRI/CRp/PR for AML patients or CR, PR, MR, PMR for MDS patients. Subjects who do not achieve CR/CRI/CRp/PR will be excluded from this analysis.

Duration of RFS is calculated as (days):

- Date of disease relapse, patient death, or censoring - Date of first Response evaluation + 1.
- Subjects without an objective disease relapse who die for any reason will be considered to have an event on the date of death. Otherwise subjects will be censored at the date of last objective response assessment showing no relapse has occurred.

Reason for censoring	Rule
Early death	Date of death
Disease progression leading to discontinuation	Date of last OR with no relapse
New anticancer treatment started before documentation of disease progression or death	Date of last radiological assessment prior to the start of non-protocol anticancer treatment

RFS will be summarized with (Mean (SD), median, min and max).

RFS will be presented graphically using Kaplan-Meier method.

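### SAP 5.7 does not stop best response at first progression, so a response or stable disease first reached after PD counts in ORR or DCR while EFS counts the same patient as progressed

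*SAP*

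**What the plan says.** SAP 5.7 builds ORR and DCR on best objective response: "Best Objective Response (BOR) = Best response obtain during the study participation for a patient". It names no end point for that window other than study participation.

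Treatment after progression is provided for. Under Protocol 9.3.2.1, "patients experiencing disease progression are permitted to continue treatment with bemcentinib where the investigator believes patients may continue to derive clinical benefit". The same section says of continued dosing: "This will not affect the time point of disease progression from the perspective of trial analysis". SAP 5.1 keeps these patients under assessment: "Any patient treated with bemcentinib beyond disease progression will be followed for the same safety and efficacy assessments as for all other patients". It also says how their data are shown: "The data for patients treated beyond progression will be presented in both a combined output (with all patients) and a separate output". For Part B, "a new period (treated beyond disease progression) will be created if the date of progression < date of any intake of the bemcentinib". That rule identifies the later data but does not remove them from BOR.

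SAP 6.3.2 lists one ORR table per part plus age and cytogenetic subgroups, with no version limited to data before PD. The only listed beyond-progression outputs are AE and SAE tables (SAP 6.3.3.1) and an AE listing (SAP 6.4).

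In SAP 5.7, EFS takes death or progression as the event. RFS runs to relapse, for which the "date of the disease progression will be used since disease progression is based in blast count assessment". Its duration is "Date of disease relapse, patient death, or censoring - Date of first Response evaluation + 1".

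Protocol 16.5.2 tests ORR against 5%, one-sided, and treats P < 0.2 as enough to justify further study.

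**The concern.** A patient who meets PD, stays on drug and later has a qualifying marrow is a responder under the BOR rule and an event under EFS. The same split can arise for disease control. Appendix 5 of the protocol defines unchanged disease reading by reading, as no remission and PD criteria not met. SAP 3.2 asks for at least 3 cycles of it but does not say that those cycles must come before PD.

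Counting such patients can only raise ORR and DCR. ORR carries the only formal test in the plan, and the result turns on 2 responders in a cohort of 14 or 3 in Part B5. RFS also has no rule for a response that comes after the progression date.

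**Working it through.** **1. The plan's own design figure.** Inputs from SAP 4.9 and Protocol 16.9: null 5%, anticipated 20%, one-sided size 0.2, power 80%, n = 14 (B1 to B4) and n = 20 (B5). Exact binomial, passing at the smallest count r with P(X ≥ r | 5%) ≤ 0.2:

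- n = 14, r = 2: P(X ≥ 2 | 5%) = 1 − 0.95^14 − 14 × 0.05 × 0.95^13 = 0.153. P(X ≥ 2 | 20%) = 1 − 0.8^14 − 14 × 0.2 × 0.8^13 = 0.802. The value 14 is reproduced; it is the smallest n that meets both limits.
- n = 20, r = 3: size 0.0755, power 0.794, close to the stated 80%.

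**2. One patient at the margin.** Upper-tail P at 5%:

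| Cohort | Without the post-PD responder | With the post-PD responder |
|---|---|---|
| n = 14 | 1/14, P = 0.512 | 2/14, P = 0.153 |
| n = 20 | 2/20, P = 0.264 | 3/20, P = 0.0755 |

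Each step crosses 0.2. One patient is 1/14 = 7.1 points of ORR, or 1/20 = 5 points in B5.

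**3. How far the pass probability could move.** The documents give no rate of post-PD response, so this step rests on an assumption. Let q be the share of patients without a pre-PD response who have a counted response after PD. With a true pre-PD rate of 5%, the counted rate is 0.05 + 0.95q.

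| q (assumed) | Counted rate | Pass, n = 14 | Pass, n = 20 |
|---|---|---|---|
| 0 | 0.050 | 0.153 | 0.0755 |
| 2% | 0.069 | 0.251 | 0.156 |
| 5% | 0.0975 | 0.403 | 0.309 |
| 10% | 0.145 | 0.624 | 0.570 |

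**4. RFS.** With 21-day cycles, Day 1 of cycle c is study day 21(c − 1) + 1, so C2D1 is Day 22 and C4D1 is Day 64. Take PD at C2D1, first response at C4D1, and that PD as the relapse date: 22 − 64 + 1 = −41 days. With PD at C4D1 (Day 64) and first response at C7D1 (Day 127): 64 − 127 + 1 = −62 days. A patient who responds, progresses and responds again is unaffected, because the first response precedes PD.

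**5. Disease control.** In Appendix 5, marrow PD in AML is a rise of more than 50% over the pretreatment blast value, that is, above 1.5 times baseline. A patient who progresses and stays above that level still meets PD at each reading. Only a patient who falls back below it, without remission, becomes unchanged again, and that status must last at least 3 cycles to count as SD.

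**The case against.** Most of the case on the other side concerns how often this happens and how strongly it may be stated, and much of it stands.

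- **Narrow route.** Protocol 12.5 requires discontinuation at PD unless the investigator, patient and sponsor agree otherwise in writing. Mandatory marrows stop once PD is confirmed (Tables 5 and 6, note k). Optional and clinically indicated ones remain. Cases will be few, but the route is open.
- **No direct contradiction with the protocol.** A reader might infer that the BOR rule breaches the Protocol 9.3.2.1 statement on the timing of progression. It does not: that sentence fixes the PD date, the BOR window leaves the date alone, and EFS still uses it.
- **Steadily worse patients.** A reader might also infer that anyone who is worse than baseline but steady becomes SD. By marrow blasts in AML this fails, as step 5 shows.
- **Negative RFS is not inevitable.** SAP 5.7 describes RFS as running from response to relapse, which most naturally means a later progression. The negative value needs the earlier PD to be taken as the relapse, and the text does not rule that out.
- **Late responses.** Protocol 12.4 reports delayed responses in this study but does not say that they followed documented PD. It is therefore not evidence that post-PD responses have occurred. It does give the sponsor a fair reason to want late responses shown.
- **Prespecified combined output, exploratory status.** The combined presentation is planned, efficacy in Part B is a secondary objective, and Protocol 16.5.2 calls the efficacy analysis exploratory. The same section nevertheless ties the ORR result to further study and, if efficacy is significant, to pivotal studies. The steps shown are the tipping points, and any reclassified patient would have the same effect there.

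**Conclusion.** The point holds as a gap in the BOR definition. Followed literally, SAP 5.7 lets a response first reached after PD, or a sustained return to unchanged status after PD, enter ORR or DCR while EFS counts the patient as progressed. It also leaves RFS undefined, and possibly negative, when PD comes before the first response.

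The direction of the effect is upward. At the margin one patient is enough to cross P < 0.2, in a cohort of 14 or in B5. Away from the margin one patient does not change the test result. The pass probabilities in step 3 depend wholly on the assumed q and should be read as a range, not a forecast. The documents do not support saying that the effect will be frequent, that the plan contradicts the protocol's fixed PD date, or that negative RFS times must occur.

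**What to change.** In SAP 5.7, state: *For the headline ORR, DCR, the ORR test and RFS, BOR is the best response from first dose up to and including first documented PD, in Parts A and B; for RFS, relapse is the first PD after the first response.* The PD date should be the one used for EFS, so that the endpoints agree.

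Keep the combined output that SAP 5.1 and Protocol 16.4.2 require, as a supplementary ORR and DCR that includes post-PD assessments. Add one beyond-progression response table or listing to SAP section 6, since none is listed now.

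The cost is one sentence, one supplementary analysis and one output. The SAP 5.1 period flag serves Part B; Part A needs the same cut derived from its PD dates. The design is unchanged: 2 of 14 at size 0.153 and power 0.802, and 3 of 20 at 0.0755 and 0.794. The downside is that late responses after documented PD leave the headline ORR, though they stay visible in the supplementary and separate outputs. A blast rise that is not judged to be PD (Appendix 5, note d) is unaffected.

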## Relapse Free Survival [RFS]

Relapse free survival [RFS]: defined as the months from the date of response until the date of relapse as confirmed by blast counts assessment (date of the disease progression will be used since disease progression is based in blast count assessment) .

Relapse Free Survival is defined only for subjects with a best objective response of CR/CRI/CRp/PR for AML patients or CR, PR, MR, PMR for MDS patients. Subjects who do not achieve CR/CRI/CRp/PR will be excluded from this analysis.

Duration of RFS is calculated as (days):

- Date of disease relapse, patient death, or censoring - Date of first Response evaluation + 1.
- Subjects without an objective disease relapse who die for any reason will be considered to have an event on the date of death. Otherwise subjects will be censored at the date of last objective response assessment showing no relapse has occurred.

Reason for censoring	Rule
Early death	Date of death
Disease progression leading to discontinuation	Date of last OR with no relapse
New anticancer treatment started before documentation of disease progression or death	Date of last radiological assessment prior to the start of non-protocol anticancer treatment

RFS will be summarized with (Mean (SD), median, min and max).

RFS will be presented graphically using Kaplan-Meier method.

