Appendix 4: CYP3A4 Substrates

Examples of CYP3A4 substrates are provided below. For most up-to-date information on CYP3A4 substrates, please check the Drug Interactions Flockhart Table™ <https://drug-interactions.medicine.iu.edu/Main-Table.aspx>.

University of Indiana CYP3A4, 5, 7 P450 Drug Interactions Abbreviated "Clinically Relevant" Table of Substrates

Macrolide antibiotics:	HIV Antivirals:	HMG CoA Reductase Inhibitors:
clarithromycin	indinavir	atorvastatin
erythromycin (not 3A5)	ritonavir	lovastatin
NOT azithromycin	saquinavir	NOT pravastatin
telithromycin	nevirapine	NOT rosuvastatin
		simvastatin
Anti-arrhythmics:	Prokinetics:	
quinidine→3-OH	cisapride	Others:
		alfentanyl
Benzodiazepines:	Antihistamines:	aripiprazole
alprazolam	astemizole	boceprevir
diazepam→3OH	chlorpheniramine	buspirone
midazolam	terfenadine	carbamazepine
triazolam	Calcium Channel Blockers:	gleevec
	amlodipine	haloperidol
Immune Modulators:	diltiazem	pimozide
cyclosporine	felodipine	quinine
tacrolimus (FK506)	nifedipine	tamoxifen
sirolimus	nisoldipine	telaprevir
	nitrendipine	trazodone
PDE-5 Inhibitors:	verapamil	vincristine
sildenafil		diergotamine & ergotamine
tadalafil		fentanyl
ildenafil		

Flockhart DA. Drug Interactions: Cytochrome P450 Drug Interaction Table. Indiana University School of Medicine (2007). "/clinpharm/ddis/clinical-table/" Accessed 20 October 2016.

Appendix 5: Modified International Working Group Response Criteria in Acute Myeloid Leukemia (Cheson, 2003, Döhner, 2017)

IWG Response Criteria in AML		Bone Marrow Blasts/Myeloblast	Circulating or Peripheral Blood Blasts ^a	Absolute Neutrophil Count	Platelet Count	EMD
Morphologic Complete Remission	CR	<5% and no myeloblasts with Auer rods	None	$\geq 1.0 \times 10^9/L$ or $\geq 1,000/\mu L$	$\geq 100 \times 10^9/L$ or $\geq 100,000/\mu L$	None
CR with Incomplete Blood Count Recovery	CRi	<5% and no myeloblasts with Auer rods	None	$<1.0 \times 10^9/L$ or $<1,000/\mu L$	$<100 \times 10^9/L$ or $<100,000/\mu L$	None
Morphologic leukemia-free state	MLFS	<5% and no myeloblasts with Auer rods ^b	No hematologic recovery required			None
Partial Remission	PR	Decrease of myeloblasts % to 5% to 25% and decrease of pretreatment myeloblast % by at least 50%	All hematologic criteria of CR			
Unchanged	UN	Absence of CR, CRi or PR and criteria for PD not met				

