Progressive Disease ^c	PD	>50% increase in myeloblasts over the pretreatment value (a minimum 15% increase is required if <30% myeloblasts pretreatment)	>50% increase in PB to $>25 \times 10^9/L$ or $>25,000/\mu L$ ^d			New EMD disease

a. PBs are quantified as an automated WBC times percentage of blasts by manual differential (100 cells) per standard clinical laboratory procedures.
 b. BM examination should not be aplastic, and have at least 200 cells or cellularity should be at least 10%
 c. PD is usually accompanied by a decline in ANC and platelets, increased transfusion requirement and decline in performance status and increase in symptoms.
 d. Certain targeted therapies may cause a differentiation syndrome, that is, a transient increase in the percentage of BM blasts (myeloblasts) and an absolute increase in PBs; in the setting of therapy with such compounds, an increase in blasts may not necessarily indicate PD.

Abbreviations: AML, acute myeloid leukemia, ANC, Absolute Neutrophil Count; BL, EMD, Extramedullary Disease; IWG, International Working Group, PB, Peripheral Blood Blast; WBC, White Blood Cell.

References

BGBC003 v10.0 (US);

Appendix 6: International Working Group Response Criteria in Myelodysplastic Syndromes (Cheson, 2006)

Category A: Altering the natural history of disease			
IWG Response Criteria in MDS	Bone Marrow ^a	Peripheral Blood ^a	Additional Considerations
Complete Remission (CR)	≤5% myeloblasts with normal maturation of all cell lines with no evidence for dysplasia ^b	Normalization of blood counts as defined by: 
 • Hb ≥11g/dL (not supported by EPO or transfusions) • Platelets ≥100 x 10⁹/L or 100,000/µL (not supported by transfusions) • Neutrophils ≥1.5 x 10⁹/L or 1,500/µL (not supported by G-CSF) • PB 0% 	Responses to be confirmed in two successive assessments; response parameters in peripheral blood needs to be maintained for at least 6 weeks.

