### 3.2 Efficacy endpoints

In AML, efficacy endpoints will be measured using objective response criteria, in evaluable patients.

- Objective Response (OR) or Stable Disease (SD) according to the revised recommendations of the International Working Group (IWG) in AML [Cheson, BGBC003 v8.0 (NO); 04 August 2020 CONFIDENTIAL Page 37 of 113 2003 and Döhner, 2017] (see Appendix 5 of the protocol). SD is defined as having unchanged disease for at least 3 treatment cycles.
- Proportion of patients with an OR + SD as an estimate of clinical benefit.
- Relapse Free Survival
- Event Free Survival
- Overall Survival
- To explore the correlation between baseline biomarker levels and clinical endpoints

In MDS, efficacy endpoints will be measured using the following response criteria.

- OR or SD according to the revised recommendations of the IWG in MDS (see Appendix 6 of the protocol). SD is defined as failure to achieve at least PR but not evidence of PD for at least 3 treatment cycles.
- Proportion of patients with an OR + SD as an estimate of clinical benefit.
- Relapse Free Survival
- Event Free Survival
- Overall Survival
- To explore the correlation between baseline biomarker levels and clinical endpoints

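### SAP 5.7 dates AML relapse by the progression date, so a marrow that returns to its pretreatment blast level after remission is not, by marrow, an RFS event

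*SAP*

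**What the plan says.** **RFS (SAP 5.7).** RFS runs from first response, in responders only: "Relapse Free Survival is defined only for subjects with a best objective response of CR/CRI/CRp/PR for AML patients", with corresponding categories for MDS. Relapse is to be confirmed by blast counts, but a parenthesis adds that the "date of the disease progression will be used since disease progression is based in blast count assessment". Death without relapse is an event on the day of death. Other patients are censored at their last response assessment without relapse. A table then lists three reasons for censoring:

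- early death, at the date of death;
- progression that leads to discontinuation, at the last response without relapse;
- new anticancer treatment before documented progression or death, at the last radiological assessment before it.

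**EFS (SAP 5.7).** The event is death or progression. Relapse is not named.

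**AML response criteria.** SAP 3.2 refers to protocol Appendix 5. There, CR and CRi need marrow blasts below 5% and no circulating blasts. Marrow PD is a ">50% increase in myeloblasts over the pretreatment value (a minimum 15% increase is required if <30% myeloblasts pretreatment". The other routes to PD are a rise of more than 50% in peripheral blasts to above 25 x 10^9/L, and new extramedullary disease (EMD). The category Unchanged is "Absence of CR, CRi or PR and criteria for PD not met". Appendix 5 has no relapse row. Appendix 6, for MDS, has one, and it includes a return to the pretreatment blast percentage. The table in SAP 6.7.1 gives relapse or death as the RFS event.

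**The concern.** The parenthesis treats relapse and progression as interchangeable because both rest on blast counts. They use different reference values. Relapse after remission is judged against the remission state (below 5%), whereas Appendix 5 marrow PD is judged against the blast level before treatment. A patient who goes from CR back to the starting level has lost the remission, yet has a 0% rise over pretreatment and so no marrow PD.

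Followed as written, the RFS rule gives such a patient no event at that visit. The event comes with a later PD or death, or the patient is censored. EFS in responders has the same gap through its own event definition. What is at stake is whether the RFS table and curve describe how long remission lasted.

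The censoring table is a second problem that does not depend on Appendix 5. It censors early deaths, although the text above it makes any death an event. It also censors progression leading to discontinuation, although the text uses the progression date as the relapse date.

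**Working it through.** The plan states no event count, power or expected duration for RFS or EFS, so there is no planned figure to reproduce. The check applies the written rules.

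**Step 1: marrow PD threshold.** Inputs are the Appendix 5 PD and PR rows. For pretreatment blasts b, the threshold is 1.5b when b is 30% or more. When b is below 30%, the 15% minimum can be read as relative (threshold 1.5b) or as percentage points (the larger of 1.5b and b + 15). The PR ceiling is the smaller of 25% and b/2, and PR also needs CR-level counts.

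| b | Marrow PD above | Gap from b (points) | PR ceiling |
|---|---|---|---|
| 20% | 30% (relative) or 35% (points) | 10 or 15 | 10% |
| 40% | 60% | 20 | 20% |
| 60% | 90% | 30 | 25% |
| 66.7% or more | 100% or more: unreachable | n/a | 25% |

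A return to b is below the threshold for every b. After CR, a marrow between the PR ceiling and the PD threshold is classed Unchanged and gives no event; these are the clearest misses. A marrow from 5% up to the PR ceiling, with CR counts, also gives no event, but there the SAP still regards the patient as responding.

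**Step 2: one assumed patient.** Cycle n Day 1 is study day 21(n - 1) + 1, so C4D1, C7D1 and C10D1 (scheduled response visits) are days 64, 127 and 190. Let b = 40%, with CR on day 64, marrow 40% on day 127 and 55% on day 190. Neither later marrow exceeds 60%. With the SAP formula (end date - first response date + 1):

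- Dated at loss of remission: 127 - 64 + 1 = 64 days, event.
- Alive at cut-off without PD: 190 - 64 + 1 = 127 days, censored. If the 40% and 55% marrows are not accepted as showing no relapse: 64 - 64 + 1 = 1 day, censored.
- Death on an assumed day 200 to 365, with no new treatment first: 200 - 64 + 1 = 137 to 365 - 64 + 1 = 302 days, event.
- New anticancer treatment between days 127 and 190, reading the radiological assessment as the last response visit: 127 - 64 + 1 = 64 days, censored. A later death then does not count.

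**Step 3: effect on a cohort curve.** At the planned 20% response rate, 0.2 x 14 = 2.8 and 0.2 x 20 = 4, so about 3 or 4 responders. If the first relapse is recorded, Kaplan-Meier falls to 1 - 1/3 = 0.67 or 1 - 1/4 = 0.75. If that relapse is censored or delayed, the curve at that time stays at 1.00 under every reading in Step 2.

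**Step 4: censoring table against text.** Any death without relapse is an event in the text; early death is a censoring reason in the table. The progression date is the relapse date in the text; progression leading to discontinuation is a censoring reason in the table. The RFS section does not define early death. SAP 5.8.1.1 uses the term for the first 4 weeks after C1D1. On that meaning the row would reach few responders, since the first scheduled response visit is day 22.

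**The case against.** **Other routes catch the relapse.** Peripheral blasts above the PD limit, new EMD or death would each give an event, and protocol 9.3.4 requires survival follow-up. This stands in part. A reader might infer that these relapses never count, and the documents do not support that: many would become late events. But death comes later than relapse, and the new-treatment row can censor the patient before it.

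**Investigators will record relapse as PD.** They may, but the protocol tells them to assess by Appendix 5, and neither document describes a separate relapse record. The analysis would then rest on an unwritten rule.

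**Not every loss of CR is relapse.** This stands. CRi keeps marrow blasts below 5% with none circulating, so a move from CR to CRi is a fall in counts. A fall to PR-range blasts is arguable too, because the SAP includes PR in the RFS population. Footnote d of Appendix 5 also warns that with some targeted therapies "an increase in blasts may not necessarily indicate PD".

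**The response tables may differ.** This stands as a limit. The SAP pools four country protocols and cites US version 9.0, while the supplied text is version 10.0. It also uses CRp, MR and PMR, which the supplied appendices do not name. Another country's appendix could hold an AML relapse row.

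**The endpoints are exploratory.** Protocol 16.5.2 says so, and no hypothesis test uses RFS or EFS.

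**Conclusion.** The point holds, with limits. Under the supplied Appendix 5, the RFS rule cannot register a return to pretreatment marrow blasts as relapse by marrow, and the censoring table contradicts the text above it. Both problems push the Kaplan-Meier RFS curve upward; the first also affects EFS in responders. EFS in patients who never responded is unaffected.

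A reader might infer that every RFS summary is flattered. The documents do not support that: SAP 5.7 also reports mean and median durations, and under one reading the example patient contributes 1 day instead of 64. A reader might also infer a known size of bias. The number of patients affected cannot be derived, and the contrast of 1.00 with 0.67 or 0.75 is for one assumed missed relapse among 3 or 4 responders, with no earlier event.

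The relapse-date part assumes that the same PD row governs all four country protocols. The censoring-table part does not need that assumption. The response-rate test and the sample size are unaffected. The correction should be made because the reported durability of remission would otherwise not measure relapse.

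**What to change.** These changes concern analysis only.

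1. Delete the parenthesis in SAP 5.7. For AML patients who reached CR, CRi or CRp, define relapse as the first assessment at which marrow blasts are 5% or more or circulating blasts reappear, or at which new EMD is recorded. State any confirmation rule, how footnote d is applied, and the blast criteria for CRp. The RFS event is the first of relapse, PD or death. Say whether CRh belongs in the RFS population: the response-rate text counts it ("CRh is defined as, CR (<5% myeloblasts and 0% blasts in the peripheral blood) with partial hematologic recovery") and the RFS text omits it.
2. For AML patients whose best response is PR, keep PD or death as the event and show them separately.
3. Remove the rows for early death and for progression leading to discontinuation from the RFS censoring table. In the new-treatment row, replace the radiological assessment with the response assessment.
4. For EFS, either count the same relapse as an event or report that as a sensitivity analysis beside the stated definition of death or progression.
5. For MDS, reconcile the Appendix 6 relapse row, which also admits falls in blood counts alone, with the SAP's requirement that relapse be confirmed by blast counts.

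The cost is SAP wording, a relapse date programmed from blast data already collected, and a split within the existing RFS table and figure. The response items listed in the protocol schedule are blasts, neutrophils and platelets, so check that EMD is captured before using it. RFS, and EFS in responders, may come out shorter. If the SAP can no longer be amended, its section 5.13 allows a justified deviation in the study report.
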